13.4.2 Timing of Radiographic Evaluations

All patients will undergo serial radiographic assessments to assess tumor response. Initial tumor imaging at screening must be performed within 28 days prior to the date of the first dose of study drug. Scans performed prior to the signing of the ICF as part of routine clinical management are acceptable for use as initial tumor imaging if they are of diagnostic quality and performed within 28 days prior to the date of first dose.

Memorial Sloan Kettering Cancer Center
[name]
[name]

Radiographic evaluations to assess extent of disease will be conducted at screening and every 8 weeks (56 ± 5 days) from Cycle 1 Day 1 for the first 12 cycles on study (or sooner if clinically indicated). Thereafter tumor assessments will be performed every 12 weeks (84 ± 7 days). Per RECIST v1.1, CR or PR should be confirmed; tumor imaging for confirmation of response must be performed at least 4 weeks after the first indication of response.

Imaging should not be delayed for delays in cycle starts or extension of combination treatment cycle intervals.

Radiographic evaluations will continue until PD, start of alternate anticancer therapy, withdrawal of consent to study participation, becoming lost to follow-up or death. If a patient discontinues treatment for a reason other than radiographic disease progression, withdrawal of consent to study, lost to follow-up, or death, scans should continue at the specified intervals until progression is confirmed or until the start of subsequent anticancer treatment.

If a patient discontinues treatment for clinical progression and does not meet RECIST v1.1 criteria for progression, scans should continue at the specified intervals until progression is confirmed or until the start of subsequent anticancer treatment.

13.4.3 Assessment of Response by RECIST

RECIST v1.1 will be used by the investigator as the primary measure for assessment of tumor response, date of disease progression, and as a basis for all protocol guidelines related to disease status.

14.0 BIOSTATISTICS

14.1 Analysis Populations

The following analysis populations will be used:

- **DLT Evaluable Population** consists of patients who receive at least 80% of planned total doses of mirdametinib in cycle 1 (in Arm 1 only, also both doses of fulvestrant) and are observed within 28 days following the first dose of mirdametinib or patients who experience a DLT.
- **Efficacy Population**, used for the assessment of efficacy for each arm, will consist of all patients in Part 2 who received at least 1 dose of study drug and who have at least 1 post-baseline tumor assessment. Arms 1 and 2 will be analyzed separately. In addition, patients treated at the MTD in the dose escalation portion of the protocol (both arms 1 and 2) will be included in the efficacy analyses for the expansion cohorts in part 2 if they meet the requirements for efficacy population as defined above. Additionally, the RP2D will be determined pending the clinical data obtained in the dose escalation portion of the protocol. If the RP2D is less than the MTD, then patients treated at the RP2D in the dose escalation portion of the protocol (both arms 1 and 2) will be included in the

Memorial Sloan Kettering Cancer Center
[name]
[name]

efficacy analyses for the expansion cohorts in part 2 if they meet the requirements for efficacy population as defined above.

- **Pharmacokinetic Population**, used for the assessment of pharmacokinetic endpoints, will consist of all patients who have sufficient pharmacokinetic concentration data recorded to derive pharmacokinetic endpoints.
- **All treated population or safety population:** consisting of all patients who receive any amount of drug

Arms 1 and 2 will be analyzed separately throughout the study.

Arm 1

The study will follow a standard 3+3 dose escalation schema. As described previously in section 4.2, the 3+3 decisions in Part 1 of Arm 1 will be made starting with a mirdametinib starting dose level (4 mg BID PO), where subjects will be treated with mirdametinib 4 mg BID PO given continuously in combination with the recommended dose of fulvestrant. If ≤ 1 of the first 3 DLT evaluable subjects in Dose Level 1 exhibit a DLT in Cycle 1, then Dose Level 1 will be expanded. Mirdametinib dose in combination with fulvestrant will not be escalated above the 4 mg BID given continuously dose level.

A sufficient number of subjects will be treated with mirdametinib 4 mg BID PO given continuously in combination with the recommended dose of fulvestrant to accrue at least 6 evaluable subjects. If ≤ 1 of 6 evaluable subjects in the starting dose level exhibit a DLT in Cycle 1, then **mirdametinib 4 mg BID PO** given continuously will be declared as the recommended dose for Part 2 (RP2D) in combination with fulvestrant. If ≥ 2 of the first 3 evaluable subjects or ≥ 2 of the 6 evaluable subjects in Dose Level 1 exhibit a DLT in Cycle 1, then the mirdametinib dose will be de-escalated (Dose Level -2). If dose de-escalation is not required there will be six evaluable patients total.

In the case of de-escalation, Mirdametinib Dose Level -2 (de-escalation dose level 2 mg BID PO) will be given to up to 3 subjects, treated with mirdametinib 2 mg BID PO given continuously in combination with the recommended dose of fulvestrant. If 1 of the first 3 evaluable subjects in Dose Level -2 exhibit a DLT in Cycle 1, then a sufficient number of subjects will be treated with mirdametinib 2 mg BID PO given continuously in combination with the recommended dose of fulvestrant to accrue 6 evaluable subjects. If 1 of 6 evaluable subjects in Dose Level -2 exhibit a DLT in Cycle 1, then **mirdametinib 2 mg BID PO** given continuously will be declared as the recommended dose for Part 2 (RP2D) in combination with fulvestrant. If ≥ 2 of the first 3 evaluable subjects or ≥ 2 of the 6 evaluable subjects in Dose Level -2 exhibit a DLT in Cycle 1, then the Arm 1 will be further de-escalated.

In this case, Mirdametinib Dose Level -2INT (de-escalation dose level at 2 mg BID PO on a 3 weeks on, 1 week off schedule) will be given to up to 3 subjects, treated with mirdametinib 2 mg BID PO on a 3 weeks on 1 week off schedule, in combination with the recommended dose of

Memorial Sloan Kettering Cancer Center
[name]
[name]

fulvestrant. If 1 of the first 3 evaluable subjects in Dose Level -2INT exhibit a DLT in Cycle 1, then a sufficient number of subjects will be treated with mirdametinib 2 mg BID PO on a 3 weeks on, 1 week off schedule, in combination with the recommended dose of fulvestrant to accrue 6 evaluable subjects. If 1 of 6 evaluable subjects in Dose Level -2INT exhibit a DLT in Cycle 1, then **mirdametinib 2 mg BID PO on a 3 weeks on, 1 week off schedule**, will be declared as the recommended dose for Part 2 (RP2D) in combination with fulvestrant. If ≥ 2 of the first 3 evaluable subjects or ≥ 2 of the 6 evaluable subjects in Dose Level -2INT exhibit a DLT in Cycle 1, then Arm 1 will be discontinued. In the case of de-escalation there will be at least 18 evaluable patients (6 from dose level 0, and 6 on two separate dose levels of de-escalation).

Arm 2

Part 1 will be conducted in three sequential Dose Level escalations according to the 3+3 design based on the incidence of dose-limiting toxicities (DLT) and the overall safety profile of the study treatments. At each step of the 3+3 design, the investigators will review all available safety and PK data in the current Dose Level and decide about the appropriate next step. The subjects will become evaluable for the 3+3 decisions if they complete Cycle 1 and receive at least 80% of assigned drug doses, or if they exhibit a DLT in Cycle 1. The starting dose of mirdametinib as single agent in each dose escalation dose level will be as follows: mirdametinib 4 mg BID PO given continuously, mirdametinib 6 mg BID PO given continuously, mirdametinib 8 mg BID PO given continuously. The de-escalation Dose Levels (Dose Level -1) may evaluate mirdametinib 3 mg BID given continuously and (Dose Level -1INT) may evaluate mirdametinib 3 mg BID given on. 3 weeks on, 1 week off schedule.

The 3+3 decisions in Part 1 of Arm 2 will be made similar to the above. Up to 3 subjects will be treated with mirdametinib as single agent at the dose of **4 mg BID PO** given continuously. If ≤ 1 of the first 3 evaluable subjects in Dose Level 1 exhibit a DLT in Cycle 1, then Dose Level 1 will be expanded. If 0 of the first 3 evaluable subjects in Dose Level 1 exhibit a DLT in Cycle 1, then the dose of mirdametinib as single agent will be escalated to Dose Levels 2 and 3 (**6 mg BID** given continuously **and 8 mg BID** given continuously) following the same rules as above. There will thus be as many as 18 evaluable patients on this arm.

The following table shows the corresponding probability of escalating given five hypothetical true risk for DLT.

True risk of DLT	0.1	0.2	0.3	0.4	0.5
Probability of escalation	0.9	0.7	0.5	0.3	0.2

Memorial Sloan Kettering Cancer Center
[name]
[name]

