4.0 OVERVIEW OF STUDY DESIGN/INTERVENTION

4.1 Design

This will be a Phase 1b / 2a open label, parallel design, platform study to evaluate the safety and tolerability, efficacy, PK and biomarkers of mirdametinib in two arms, where each arm will include two parts:

- Arm 1: mirdametinib in combination with fulvestrant in postmenopausal patients with estrogen receptor positive metastatic breast cancer harboring NF1 loss of function or another alteration of the MAPK pathway
 - Part 1: safety run-in (confirmation of the RP2D for mirdametinib in combination with the standard recommended dose of fulvestrant). This part may include the mirdametinib dose de-escalation according to the 3+3 design if necessary
 - Part 2: dose expansion cohorts where the mirdametinib RP2D will be administered in combination with the standard recommended dose of fulvestrant
- Arm 2: mirdametinib as single agent in adult patients with advanced solid cancers driven by the alteration of the MAPK pathway

Memorial Sloan Kettering Cancer Center
[name]
[name]

- Part 1: mirdametinib dose escalation to MTD or RP2D according to the 3+3 design
- Part 2: dose expansion cohorts

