- d. If ≥ 2 of the first 3 evaluable subjects or ≥ 2 of the 6 evaluable subjects in Dose Level 2 exhibit a DLT in Cycle 1, then **mirdametinib 4 mg BID PO** given continuously will be declared as the recommended dose for Part 2 (RP2D).

6. Dose Level 3 (Dose Level escalation **8 mg BID PO** given continuously)

- a. Up to 3 subjects will be treated with mirdametinib as a single agent at the dose of **8 mg BID PO** in Dose Level 3
- b. If ≤ 1 of the first 3 evaluable subjects in Dose Level 3 exhibit a DLT in Cycle 1, then a sufficient number of subjects will be treated with mirdametinib **8 mg BID PO** given continuously to accrue 6 evaluable subjects.
- c. If ≤ 1 of 6 evaluable subjects in Dose Level 3 exhibit a DLT in Cycle 1, then **mirdametinib 8 mg BID PO** given continuously will be declared as the recommended dose for Part 2 (RP2D).
- d. If ≥ 2 of the first 3 evaluable subjects or ≥ 2 of the 6 evaluable subjects in Dose Level 3 exhibit a DLT in Cycle 1, then **mirdametinib 6 mg BID PO** given continuously will be declared as the recommended dose for Part 2 (RP2D).
- e. The dose of mirdametinib as single agent will not be escalated above **8 mg BID PO** given continuously.

Arm 2 – Part 2 (expansion cohorts for mirdametinib as single agent)

One or more expansion cohorts (up to 30 subjects each) will be started, either in parallel or sequentially depending on the results of Part 1. The purpose will be to evaluate the efficacy and safety of the RP2D of mirdametinib as single agent (as determined in Part 1 of Arm 2) in the subjects with advanced solid cancers (with the exception of colorectal, small bowel, biliary and ampullary cancers) harboring activating mutations in MEK1/2.

Memorial Sloan Kettering Cancer Center
[name]
[name]

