For the initial parts of both arms, these utilize 3+3 design with arm 1 utilizing dose de-escalation as necessary, and arm 2 utilizing this design to escalate to MTD or RP2D. In the dose expansion cohorts of arm 1, the mirdametinib RP2D will be administered in combination with the standard recommended dose of fulvestrant with the primarily efficacy endpoint, and in dose expansion cohorts of arm 2, the mirdametinib will be given as monotherapy at the RP2D. Per MSKCC clinical research guidelines in CR426, "Expansion Cohorts in Phase I Clinical Trials", for expansion cohorts of size less than 30, a sample size justification is not required. Further, requirements for stopping rules for lack of efficacy (futility) are also not required for cohorts of less than 30 patients. Assuming a 10% low unpromising response rate (null hypothesis), and a response rate $\geq 25\%$ as a promising rate of response (alternative hypothesis), and $n = 28$ in each expansion cohort, this will provide 86% power to reject the null hypothesis if at the end of the trial at least 5 / 28 responses are observed in each cohort. Type I error is 14% for each

expansion cohort. The 10% null response rate is justified as an approximation of the standard historical rate in breast tumors treated with fulvestrant. For example, the null response rate in Solar-1 trial was 12.8%³³ and the null response rate in the Paloma-3 trial was 6.3%.³⁴

The two arms of the study will be statistically analyzed separately. Given the type I error above of 14% for any one expansion cohort, each arm (with at most two cohorts) yields a family wise error rate of $1-(1-0.14)^2 = 26\%$. If one chooses to consider the (at most) four expansion cohorts simultaneously, this yields an overall family wise error rate of $1-(1-0.14)^4 = 45\%$. While we acknowledge that this is high when all expansion cohorts are considered, first these cohorts are exploratory and second the two arms are clearly biologically different and are being treated with differing drug regimens, therefore they will be analyzed separately, thus the appropriate family wise error rate to consider for this study is that of 2 expansion cohorts, or 26%.

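### Section 14.1 does not remove Part 1 patients treated at the MTD from the expansion efficacy analysis when the RP2D is set below the MTD, so in that one case the response rate would mix two doses

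*Combined protocol and SAP*

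**What the plan says.** The Efficacy Population in 14.1 starts from Part 2: it "will consist of all patients in Part 2 who received at least 1 dose of study drug" and have at least one tumor assessment after baseline. Two inclusion rules for Part 1 patients follow.

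- The first carries no dose condition: "patients treated at the MTD in the dose escalation portion of the protocol (both arms 1 and 2) will be included in the efficacy analyses". This refers to the analyses of the Part 2 cohorts, and the patients must meet the same evaluability requirements.
- The second is conditional. After saying that the RP2D will depend on the clinical data from escalation, 14.1 continues: "If the RP2D is less than the MTD, then patients treated at the RP2D in the dose escalation portion of the protocol" join the same analyses.

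Part 2 itself uses one dose per arm. Section 14.5 says that in Arm 1 "the mirdametinib RP2D will be administered in combination with the standard recommended dose of fulvestrant", and that in Arm 2 "the mirdametinib will be given as monotherapy at the RP2D". Section 4.2 gives the aim of the Arm 2 expansion: "The purpose will be to evaluate the efficacy and safety of the RP2D of mirdametinib as single agent".

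On how the two doses relate, 4.1 describes Arm 2 Part 1 as "mirdametinib dose escalation to MTD or RP2D according to the 3+3 design". The numbered decision rules in 4.2 declare only an RP2D and never an MTD.

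**The concern.** If the RP2D is set below the MTD, both inclusion rules apply as written. The analysis set for a cohort then contains Part 2 patients at the RP2D, Part 1 patients at the RP2D, and Part 1 patients at a higher dose that was not carried forward. No efficacy analysis by dose level is specified that would separate them.

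The expansion cohorts are judged by whether at least 5 of 28 patients respond. The error rates that 14.5 gives for this rule assume one response rate for all 28. If activity rises with dose, responses at the higher dose count in favour of a dose that did not produce them. The study is also open-label. A membership rule that can be read two ways could be settled after the responses are known.

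**Working it through.** **1. The two rules side by side.** The MTD sentence has no "if". The RP2D sentence has one, but no word such as "instead", and no other text drops the MTD patients.

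| Case | Part 1 patients pooled under the literal text | Doses in the analysis |
|---|---|---|
| RP2D equals MTD | those at that dose | one |
| RP2D below MTD | those at the MTD and those at the RP2D | two |

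**2. Can the second case occur?** Under the numbered rules in 4.2 alone, no.

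- Arm 1: 4 mg BID with at most 1 DLT in 6 is declared the RP2D, and there is no escalation beyond it. With 2 or more DLTs, the dose was not cleared.
- Arm 2: the last cleared level among 4, 6 and 8 mg BID is declared the RP2D.

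The case opens only through 14.1, which foresees an RP2D below the MTD, and through the review of all safety and PK data that 4.2 requires at each step. Section 3.2 reports a precedent with this drug. In the earlier solid-tumor trial the continuous-schedule MTD was 15 mg BID, but 10 mg BID on a 5-days-on, 2-days-off schedule was recommended because of ocular events after Cycle 1. Section 15.3 here counts DLTs in Cycle 1 only.

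**3. The plan's own figures.** Inputs from 14.5: n = 28, threshold 5 responses, null rate 10%, alternative rate 25%.

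- P(X ≥ 5) for X ~ Binomial(28, 0.10) = 0.1421 (stated type I error 14%).
- P(X ≥ 5) for X ~ Binomial(28, 0.25) = 0.8646 (stated power 86%).

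Both reproduce.

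**4. Effect of mixing.** Let k of the 28 be Part 1 patients at the higher dose with response rate q, and let the other 28 − k have the null rate of 10%. Then

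P(X + Y ≥ 5), with X ~ Binomial(28 − k, 0.10) and Y ~ Binomial(k, q) independent,

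and expected ORR = [(28 − k) × 0.10 + k × q] / 28.

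The values of k come from 4.2. An expanded dose level has 6 evaluable patients. An even split of 6 over an arm's two genotype cohorts gives 3. The documents give no response rate by dose, so q is an assumption. The total is held at 28 so that only the mixing of doses changes. Section 14.1 does not say whether pooled patients count within the 28.

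| q at the higher dose | k = 3: P(≥ 5) | k = 3: expected ORR | k = 6: P(≥ 5) | k = 6: expected ORR |
|---|---|---|---|---|
| 10% (no dose effect) | 14.2% | 10.0% | 14.2% | 10.0% |
| 20% | 19.1% | 11.1% | 24.7% | 12.1% |
| 25% | 21.8% | 11.6% | 30.6% | 13.2% |

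For example, with k = 6 and q = 25%, expected ORR = (22 × 0.10 + 6 × 0.25) / 28 = 3.7 / 28 = 13.2%.

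**The case against.** The strongest reply is that the situation is not reachable. Every numbered branch in 4.2 fixes the RP2D as the highest cleared dose, and if no separate MTD is ever declared, the first sentence of 14.1 brings in nobody above the RP2D. This stands as far as 4.2 goes, and it makes the point conditional. It does not remove the point, because 14.1 writes a rule for exactly this case. If the case cannot occur, the conditional sentence has no function, and the first rule still rests on a dose that 4.2 does not name.

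The second reply is that the authors meant replacement: MTD patients by default, RP2D patients if the RP2D is lower. That is a sensible reading and may well be the intention. The text does not say it, and stating it costs one sentence.

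The third reply concerns size, and most of it stands. Having all 6 patients in one cohort is the upper end. Each arm has two genotype cohorts, and 4.2 expects Arm 2 Part 1 to accrue both MEK classes, although it allows that one class may clearly predominate at first. The assumed 25% spans the whole gap from null to alternative. Efficacy is a secondary objective, the cohorts are called exploratory, and the plan openly accepts 14% error per cohort.

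A reader might infer that the trial will report a mixed-dose response rate, or that the true type I error is 31% rather than 14%. The documents support neither. The 14% and 86% are correct for a single-dose cohort of 28, and nothing shows that the RP2D will differ from the MTD.

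**Conclusion.** The point holds in a conditional form. If the RP2D is set below the MTD, the literal text of 14.1 pools two dose groups from Part 1 into an analysis meant to describe the RP2D. If the two doses coincide, as the rules in 4.2 alone would have it, there is no effect.

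The size depends on response rates that the documents do not give. With 10% at the RP2D and 20-25% at the higher dose, the chance of calling an inactive RP2D promising is 19-22% with 3 higher-dose patients and 25-31% with 6 in one cohort. With equal rates it stays at 14.2%. Expected ORR rises by 1.1 to 1.6 points with 3 such patients and by 2.1 to 3.2 points with 6. This is a gap in the definition of the analysis population, not an arithmetic error, and it is worth closing before efficacy data are seen.

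**What to change.** Replace the two inclusion sentences in 14.1 with one. It should say that only Part 1 patients assigned to the dose and schedule declared as the RP2D, whose alteration matches the cohort and who meet the evaluability requirements, are added to that cohort's efficacy analysis. Add that efficacy at any other Part 1 dose is reported separately by dose level. With this wording the rule no longer depends on an MTD that 4.2 does not declare.

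The change affects neither treatment nor the 5-of-28 rule. Its cost is that a few Part 1 patients, at most about 6 per arm and none if the RP2D equals the MTD, move from the pooled analysis to a by-dose summary.

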14.2 General Principles

The majority of the analysis will be descriptive in nature. Unless stated otherwise, continuous variables will be summarized using descriptive statistics (number of patients, mean, standard deviation, median, lower and upper quartile, minimum and maximum values) and the number and percentage of patients will be used for categorical variables.

14.3 Safety Analysis

All AEs will be listed, including the verbatim description per CTCAE v5.0. This analysis will be done on the safety population.

TEAEs are defined as those occurring after the first dose of study drug and within 30 days following the cessation of treatment, whether or not they are considered related to the study medication.

The following key safety parameters will be evaluated:

- Incidence of TEAEs, treatment-related TEAE, TEAEs leading to death, SAE, treatment-related SAE, TEAE leading to study drug discontinuation, TEAE leading to dose modifications (e.g., dose reduction) and TEAE leading to study discontinuation
- TEAEs will be further summarized by severity (according to NCI CTCAE Version 5.0)
- Changes in clinical laboratory parameters (hematology, chemistry, urinalysis), CTCAE graded laboratory toxicities, vital signs, ECOG performance status, ECG parameters, physical examinations, ophthalmology examinations, and usage of concomitant medications

14.4 QTc Analyses

Descriptive statistics and categorical analyses of ECG variables will be provided.

14.5 Efficacy Analyses

The primary efficacy analyses will be performed using the Efficacy Population.

Efficacy endpoints will be based on RECIST v1.1 by investigator's assessment:

- **Objective Response Rate (ORR)** is defined as the proportion of patients with confirmed CR or PR (i.e., 2 visit responses of either CR or PR at least 4 weeks apart) according to RECIST v1.1 criteria.
 - The maximum percent reduction in tumor size will also be presented as a waterfall plot.
- **Clinical Benefit Rate (CBR)** is defined as the proportion of patients with a confirmed best response of CR or PR, or SD that is sustained for at least 4 months after the first dose of mirdametinib according to RECIST v1.1 criteria.

- **Duration of Response (DOR)** (applicable only to patients with confirmed CR or PR) is defined as the time interval between the date of the earliest qualifying response (CR or PR) and the date of disease progression or death for any cause, whichever occurs earlier.
 - For patients who are alive without disease progression following response, DOR will be censored on the date of last evaluable tumor assessment or last follow-up for disease progression.
- **Progression-Free Survival (PFS)** is defined as the time from the first day of study drug administration (Day 1) to disease progression as defined by RECIST v1.1 criteria, or death from any cause.
 - Patients who are alive and free from disease progression will be censored at the date of their last tumor assessment.

For ORR and CBR, patients without a post-baseline tumor assessment will be excluded as they are not efficacy evaluable. The ORR and CBR calculation will include only efficacy evaluable patients.

An exact binomial 95% confidence interval for CBR and ORR will be calculated in each treatment group using the Clopper-Pearson method.

For PFS, Kaplan-Meier curves will be generated, and the median time-to-event and the associated 95% CIs will be provided. In addition, the rate of PFS at 6 months will be derived from the corresponding Kaplan-Meier curves and the associated 95% CIs calculated using Greenwood's formula on the $\ln[-\ln(\text{survival scale})]$ and back transformed. This analysis will include the patients in the efficacy population.

Depending on responses seen, a central review of all images may also be performed by an independent reviewer as a sensitivity analysis.

Sample size justification and patient numbers.

For the initial parts of both arms, these utilize 3+3 design with arm 1 utilizing dose de-escalation as necessary, and arm 2 utilizing this design to escalate to MTD or RP2D. In the dose expansion cohorts of arm 1, the mirdametinib RP2D will be administered in combination with the standard recommended dose of fulvestrant with the primarily efficacy endpoint, and in dose expansion cohorts of arm 2, the mirdametinib will be given as monotherapy at the RP2D. Per MSKCC clinical research guidelines in CR426, "Expansion Cohorts in Phase I Clinical Trials", for expansion cohorts of size less than 30, a sample size justification is not required. Further, requirements for stopping rules for lack of efficacy (futility) are also not required for cohorts of less than 30 patients. Assuming a 10% low unpromising response rate (null hypothesis), and a response rate $\geq 25\%$ as a promising rate of response (alternative hypothesis), and $n = 28$ in each expansion cohort, this will provide 86% power to reject the null hypothesis if at the end of the trial at least 5 / 28 responses are observed in each cohort. Type I error is 14% for each

expansion cohort. The 10% null response rate is justified as an approximation of the standard historical rate in breast tumors treated with fulvestrant. For example, the null response rate in Solar-1 trial was 12.8%³³ and the null response rate in the Paloma-3 trial was 6.3%.³⁴

The two arms of the study will be statistically analyzed separately. Given the type I error above of 14% for any one expansion cohort, each arm (with at most two cohorts) yields a family wise error rate of $1-(1-0.14)^2 = 26\%$. If one chooses to consider the (at most) four expansion cohorts simultaneously, this yields an overall family wise error rate of $1-(1-0.14)^4 = 45\%$. While we acknowledge that this is high when all expansion cohorts are considered, first these cohorts are exploratory and second the two arms are clearly biologically different and are being treated with differing drug regimens, therefore they will be analyzed separately, thus the appropriate family wise error rate to consider for this study is that of 2 expansion cohorts, or 26%.

In the safety run in of arm 1, a minimum of six and as many as 12 DLT-evaluable patients are required. In the dose expansion cohorts of arm 1, the mirdametinib RP2D will be administered in combination with the standard recommended dose of fulvestrant with the primarily efficacy endpoint, and in dose expansion cohorts of arm 2, the mirdametinib will be given as monotherapy at the RP2D. For these expansion cohorts, as explained above, each will be deemed promising if at the end of the study at least 5 / 28 responses (CR or PR) are observed. This part of the study will enroll $2 * 28 = 56$ efficacy evaluable patients (28 patients on each of two expansion cohorts). Exploratory future cohorts, such as subjects with hormone receptor-positive, HER2-negative metastatic breast cancer exhibiting OncoKB defined activating mutations in BRAF, CRAF, or MEK1/2 (section 4.2) are not included in this analysis. To account for non-evaluable patients, we will have a goal total enrollment of 60 patients. This part of the study is planned to accrue approximately 2 patients per month and it is expected to complete accrual in 3 years.

In the dose escalation part of arm 2 (mirdametinib monotherapy in MEK1/2 mutant patients), we anticipate as few as 6 DLT-evaluable patients and as many as 18 DLT-evaluable evaluable patients will be required, the precise number of patients enrolled in this arm is pending the observed toxicity of mirdametinib monotherapy in dose escalation. This part of the study will take approximately nine months to complete accrual, assuming two patients per month are accrued. The specific expansion cohorts for this arm of the trial are pending the observed responses by genotype and cancer lineage in this arm of the protocol. However, as with arm 1, as explained above, each expansion cohort will be deemed promising if at the end of the study at least 5 / 28 responses (CR or PR) are observed. As we also anticipate as many as two expansion cohorts of patients on this arm of the study, this arm will also require as many as $2 * 28 = 56$ efficacy evaluable patients with a goal total enrollment of 60 patients which will take 3 years to accrue.

